Robotic-assisted surgery (RAS) represents a further step in this evolution. These systems, which use a navigated robotic arm to assist screw placement, aim to enhance accuracy and reduce variability—which may be especially beneficial for less experienced surgeons. RAS may also streamline intraoperative workflow and support minimally invasive approaches. While early results are promising, there remains limited evidence on the broader clinical benefits, especially during the early learning phase of implementation [4]. Robotic-assisted spine surgery is not sanctioned by the Swedish Association of Authorities and Regions, unless performed in clinical trials.

This study aims to evaluate the clinical introduction of robotic systems in spine surgery, focusing on their impact on reoperations, screw placement accuracy, complications, outcome, and intraoperative workflow.

7. Objectives

This study has three main objectives, analysed in three different substudies: To study screw placement accuracy, learning curve, and reoperations.

Secondary Objectives: To assess complications, patient-reported outcomes, length of stay, surgical time, and cost-effectiveness.

8. Trial Design

Multicenter, non-randomized observational cohort study with consecutive patient inclusion.

9. Study Setting

All hospitals in Sweden performing spinal surgery will participate.

10. Eligibility Criteria

Inclusion Criteria:

- Treatment with pedicle screws in the cervical, thoracic, lumbar spine and/or sacrum.
- All ages and spinal diagnoses

Exclusion Criteria:

- Treatment without pedicle screws

Consent

-All patients will be treated according to each hospital's routine. Patient consent will therefore not be needed.

11. Interventions

Experimental Group: Robotic-assisted pedicle screw insertion using available equipment. Currently available systems are Brainlab Cirq and Mazor Robotics, but others systems may be used.

Control Group: Patients undergoing non-robotic-assisted (freehand or navigation-assisted) pedicle screw placement.

12. Outcomes

Primary objectives and outcomes

Substudy 1 primary outcome - Screw placement accuracy (binary per-patient outcome)

- Proportion of patients in which at least one screw is not accurately placed.

Substudy 2 primary outcome- Learning curve (surgical time)

-To evaluate when time in surgery is no longer decreasing in robotic-assisted surgery.

Substudy 3 primary outcome - Reoperation rate at 2 years

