-The primary outcome is the occurrence of reoperations of any cause within 2 years from the index surgery in patients undergoing robotic-assisted surgery compared to non-robotic-assisted (navigation-assisted or free hand) surgery.

Secondary Outcomes

- Intraoperative (screw placement precision, including comparisons preoperative and postoperative positioning for screws and rods, surgical time; skin-to-skin as well as wheel-in wheel-out time, estimated patient radiation exposure, intraoperative bleeding)
- Postoperative outcomes (length of stay, patient-reported outcome measures (PROMs), time to return to work)
- Cost-effectiveness and procedural resource use
- Complications (care related infections, thrombosis, emboli, cardiovascular, mortality)

Table 1

Table over data collection and source.

	Radiographic data	Reoperations	Intraoperative metrics	Postoperative outcomes; complications, PROMs
Data source	PACS	SPOR, Swespine, NPR	SPOR/Surg planning program/Electronic health records	Swespine, SFR, SPOR, Electronic health records
Data origin	Radiology department	Surgeon, Anesthesiologist, Hospital	Surgeon/Anesthesiologist	Patient
Need for separate assessment	Yes, radiographic assessment by the investigators	No	No	No
Time points for data collection	Preoperative, intraoperative, postoperative, up to 2 years	Postoperative, within 2 years	Intraoperative	Preop and up to 2 years postoperative

[figure not shown]
Swespine: Swedish Spine Register

SFR: Swedish Fracture Register

SPOR: Swedish PeriOperative Register

13. Participant Timeline

Figure 1. Participant timeline. Data will be collected up to 5 years postoperative.

14. Sample size

Substudy 1- Primary outcome- Screw placement accuracy (binary per-patient outcome)

Accurate screw placement is defined as a pedicle screw that remains entirely within the cortical boundary of the pedicle, or with up to 2 mm breach of the pedicle wall (corresponds to Gertzbein-Robbins Grade A and B) [5]. To evaluate screw placement accuracy, we will define a binary per-patient outcome: whether at least one screw is not accurately placed.

Based on previous literature, robotic-assisted systems may achieve clinically acceptable accuracy per screw (Gertzbein-Robbins Grade A and B) of approximately 97%, while navigated systems achieve approximately 93% [6], and freehand 84-90% [7, 8].

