Assuming a minimum of 4 screws per patient, the estimated probability of at least one non-clinically acceptable screw is 12% in the robotic group and 25% in the navigated and free hand group.

Using a two-sided alpha of 0.05, 80% power, and a 1:6 group ratio, the required sample size is 71 patients in the robotic-assisted surgery group and 426 patients in the non-robotic-assisted surgery group, for a total of 497 patients. We added patients to 75 in the robotic-assisted surgery group, for a total of 501 patients, to be able to include an equal number of patients from Örebro, Umeå and Uppsala. This estimate is conservative, as most patients are expected to receive more than 4 screws, which would increase the likelihood of detecting placement differences.

The primary analysis will use either mixed-effects logistic regression or logistic regression with cluster-robust standard errors to account for intra-patient correlation of screw outcomes.

A secondary analysis of robot-assisted surgeries after the first 501 patients may be performed.

Substudy 2 - Primary outcome - Learning curve (surgical time)

To evaluate the learning curve associated with robotic-assisted surgery, we will model operative time as a function of case number. Operative time is expected to decrease with experience, then plateau. We will use mixed-effects piece-wise linear regression with the surgeon as a random effect to estimate the case number at which operative time levels off. We will look both at wheel-in wheel-out time (primary), and skin-to-skin time (secondary). We expect to do this analysis after each center has performed 100 robot-assisted spine surgeries, in total 300 surgeries.

We have not conducted a traditional power analysis for this substudy, as the objective is not to test a binary hypothesis but to estimate when operative time stabilizes. If no clear inflection point is observed, this will be interpreted as evidence that the learning curve is either very short (already completed), very gradual, or inconsistent. Such a result would itself be informative, and will require us to compare operative times with today's standard of care, navigated or free hand surgery.

Substudy 3- Primary outcome – Reoperation rate at 2 years

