In the primary analysis, 1:2 nearest-neighbor matching without replacement will be used, with a caliper of 0.2 standard deviations of the logit of the propensity score. Covariate balance after matching will be evaluated using standardized mean differences (SMDs), with $SMD < 0.1$ considered acceptable. Outcome analysis will be performed using Cox proportional hazards regression with robust standard errors to account for matched pairs.

As a secondary analysis, IPW will be used to create a pseudo-population in which treatment assignment is independent of observed covariates. Stabilized weights will be applied, and outcome analysis will be conducted using weighted regression models, adjusted for baseline covariates to enhance robustness.

Although both methods are suitable for dealing with moderate imbalances in group size, it is important to note that reducing the size of the non-robotic group may limit the number of matches available during PSM and could increase variance in the IPW analysis if extreme weights arise. These risks will be mitigated through careful diagnostics, including evaluation of match yield, standardized mean differences, and weight distributions. Overlap weighting or trimming will be considered if weight instability is detected.

While the study is powered at 80% based on the reduced cohort, adjusted analyses using propensity score methods may yield a slightly reduced effective sample size due to matching inefficiency or variance inflation. However, both approaches are expected to preserve sufficient power to detect the prespecified effect size, given the projected event rate and available sample size.

Multiple imputation will be used to handle missing baseline data, and all patients will be included in the final analysis. An increased proportion of robotic surgeries relative to non-robotic surgeries will decrease the overall sample size requirement to detect the same effect.

Secondary outcome - Screw placement precision

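### Substudy 1's primary model corrects for correlation between screws within a patient, but the primary outcome and sample size have one value per patient, so unit of analysis and estimand are left open

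*Protocol*

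**What the plan says.** Section 12 gives the Substudy 1 primary outcome as "Proportion of patients in which at least one screw is not accurately placed". Section 14 repeats it: "we will define a binary per-patient outcome: whether at least one screw is not accurately placed".

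The sample size in section 14 starts from per-screw accuracy, described for robotic systems as "clinically acceptable accuracy per screw (Gertzbein-Robbins Grade A and B) of approximately 97" per cent and for controls as "navigated systems achieve approximately 93% [6], and freehand 84-90% [7, 8"]. With 4 screws as the minimum, this is turned into per-patient event rates of 12% and 25%. The requirement is 71 robotic and 426 non-robotic patients (two-sided 0.05, 80% power, 1:6), raised to 75 and 426. The text adds: "This estimate is conservative, as most patients are expected to receive more than 4 screws".

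The analysis sentence follows. It offers two models for the primary analysis, a mixed-effects logistic model or "logistic regression with cluster-robust standard errors to account for intra-patient correlation of screw outcomes".

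Section 20 lists adjustment variables for the study as a whole, among them number of screws and hospital.

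**The concern.** The outcome and the sample size count patients, whereas the stated reason for the model is a feature of data with one row per screw. A statistician following the analysis sentence must first choose the row. Patient rows make the correlation clause pointless or, with a patient random intercept, leave the effect undetermined. Screw rows change the quantity being estimated. The sentence also offers two models, so the choice can be made after the data are seen, in a study without randomisation or blinding. One of the three primary results would then have no fixed estimand.

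The sample size has a related inconsistency. The event rates are derived as if screws within a patient were independent, and the analysis sentence then says that they are correlated. Calling the sample size conservative counts the gain from more screws but not the loss from correlation.

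**Working it through.** **1. Reproducing the plan's figure.** Inputs from section 14: per-screw error 3% (robotic) and 7% (navigated), 4 screws, two-sided 0.05, 80% power, 1:6.

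- Robotic: 1 − 0.97^4 = 0.1147 (stated as 12%).
- Control: 1 − 0.93^4 = 0.2519 (stated as 25%).
- Arcsine effect size: h = 2·asin(√0.2519) − 2·asin(√0.1147) = 1.0517 − 0.6910 = 0.3607.
- n = (1.960 + 0.842)² × (1 + 1/6) / h² = 70.4, so 71 robotic and 6 × 71 = 426 controls.

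The same formula gives 419.01 and 865.5 for the two Substudy 3 scenarios, matching the stated 420 and 866, so it is very probably the method used. The 71:426 is therefore a comparison of two per-patient proportions. Outcome and sample size agree, and the analysis sentence is the part out of line.

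**2. Patient rows, patient random intercept.** With treatment as the only covariate, the data determine two arm probabilities, but the model has three parameters (intercept, treatment effect, random-intercept SD). In a simulated data set of 75 + 426 patients:

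| SD fixed at | Maximised log-likelihood | Treatment log-odds ratio |
|---|---|---|
| 0 | −259.9447 | −0.97 |
| 1 | −259.9447 | −1.10 |
| 2 | −259.9447 | −1.44 |
| 3 | −259.9447 | −1.88 |

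The fit is the same throughout, while the odds ratio runs from exp(−0.97) = 0.38 to exp(−1.88) = 0.15.

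**3. Patient rows, patient-clustered standard errors.** In the same data, the standard errors of intercept and treatment effect are 0.1135 and 0.3909 with clustering by patient, and the same with ordinary robust errors. The model fits and the clustering does nothing.

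**4. Screw rows.** Both models can now be fitted, but they compare 3% with 7% per screw. With 4 screws each, there are 75 × 4 = 300 and 426 × 4 = 1,704 screws. Dividing by the design effect 1 + 3 × ICC gives a power of 80.4% at ICC 0, 66.8% at 0.1 and 46.5% at 0.3 (ICCs assumed; the Protocol gives none).

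**5. Independence and the word conservative.** Let screws in a patient follow a beta-binomial with per-screw error p and intraclass correlation ρ. With a = p(1−ρ)/ρ and b = (1−p)(1−ρ)/ρ, the risk of at least one inaccurate screw among k is 1 − ∏ (b+i)/(a+b+i), for i = 0 to k−1. For p = 0.07, ρ = 0.1, k = 4: b = 8.37, a + b = 9, and the product is (8.37 × 9.37 × 10.37 × 11.37)/(9 × 10 × 11 × 12) = 0.778, so the risk is 22.2%. Power is for the two-sided score test at 75:426, summed over all possible outcomes:

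| Screws per patient | ICC (assumed) | Robotic | Control | Power |
|---|---|---|---|---|
| 4 | 0 | 11.5% | 25.2% | 79% |
| 4 | 0.1 | 10.0% | 22.2% | 72% |
| 4 | 0.2 | 8.8% | 19.7% | 66% |
| 6 | 0.1 | 13.6% | 29.3% | 86% |
| 6 | 0.2 | 11.4% | 24.9% | 78% |

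The score test starts slightly below the arcsine approximation, which gives 82.1% at 75:426 with independent screws.

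**6. Screw count.** The any-screw outcome rises with construct length whatever the technique: 1 − 0.97^10 = 26.3% for ten robotic screws, close to the 25.2% for four navigated screws. The unadjusted per-patient comparison therefore depends on how many screws each arm receives.

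**The case against.** The strongest reply is that one of the two named models already works. Logistic regression with cluster-robust errors on one row per patient fits and targets the declared outcome. That stands: a reader might infer that the primary analysis cannot be run at all, and this is not so. What remains is that its stated purpose is void on patient rows, and that the other option is unidentifiable there.

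It can also be said that the two odds ratios are numerically close. At 4 independent screws the per-patient value is (0.1147/0.8853)/(0.2519/0.7481) = 0.385 and the per-screw value (0.03/0.97)/(0.07/0.93) = 0.411. They are still different quantities: at 10 screws the per-patient value is (0.2626/0.7374)/(0.5160/0.4840) = 0.334, while the per-screw value stays the same. Precision differs as well.

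A reader might infer that screw count is ignored. It is not: section 20 lists it as an adjuster, so the ten-versus-four example is an unadjusted contrast that the Protocol does not plan. The Substudy 1 model sentence merely omits it.

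A reader might also infer that the substudy is underpowered. The Protocol does not support this. Four screws is its minimum, and controls include freehand cases with lower accuracy. With an assumed control error of 8.5% (an equal mix of 93% and 90% accuracy), power at 4 screws is 92.5% at ICC 0.1 and 88.4% at ICC 0.2.

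Finally, no surgeon term is named for Substudy 1, although Substudy 2 has one. Hospital adjustment covers part of that clustering, a surgeon term can be left to a statistical analysis plan, and the Protocol gives no figures from which to size the effect. This is not counted as an error, here or for the Substudy 3 Cox model.

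**Conclusion.** The Substudy 1 analysis sentence contradicts the outcome and sample size in the same document. It justifies the primary model by a correlation that a per-patient outcome cannot have, and it leaves both model and row unit open. This follows from the text and needs no assumption. The sample size of 71:426 is coherent with the declared outcome and is not in question on this ground.

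The word conservative is unproven rather than wrong. The 12% and 25% require independent screws. Once correlation is admitted, power depends on two opposing forces: from 66% to 86% over 4 to 6 screws and ICC 0.1 to 0.2, with all controls at the navigated error rate. The ICCs and the beta-binomial form are assumptions.

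**What to change.** In section 14, Substudy 1:

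- Name a single primary model: logistic regression with one row per patient, any inaccurate screw as the response, the section 20 adjusters that apply, and number of screws written in explicitly. Delete the clause on intra-patient correlation from it.
- Move the screw-level model (mixed-effects or cluster-robust, one of them chosen in advance) to a secondary analysis, described as estimating a per-screw odds ratio.
- Replace the unqualified claim that the estimate is conservative with a short power table over screw counts and within-patient ICCs, and state that the 12% and 25% assume independent screws.
- Optionally, add surgeon-clustered standard errors as a sensitivity analysis.

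The cost is a few sentences and one table. The sample size stays at 75:426, and number of screws is already a listed adjustment variable, so no new data are needed.

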We will evaluate screw placement precision as the deviation between preoperative planning and actual placement in robotic-assisted surgery cases. For each screw, linear deviation (at the tip and tail) perpendicular from the planned position, to the actual position, and angular deviation between the planned position and the actual position will be measured. This comparison will be made on an overlay of the preoperative planning made on a preoperative computed tomography, and compared with the computed tomography performed intra- or postoperative for assessment of pedicle screw position.

Stratified comparisons (e.g., by spinal level or surgeon experience) may be performed to identify patterns of deviation. We plan to use the first 60 cases in the study in each of 3 centers that perform robotic-assisted spine surgery for this analysis, and for comparison divide them into a first ($n=30*3$) and second group ($n=30*3$), in all 180 cases.

Other secondary outcomes

Other complications

Thromboembolic, cardiovascular complications and mortality will be assessed as secondary safety outcomes. These events are rare in spine surgery, and although the study is not powered to detect small differences in such outcomes, comparisons between robotic and non-robotic cohorts will be reported.

Other outcomes

Length of stay, time to return to work will be described, but no power calculation has been made.

Health economic analysis

A health economic analysis will be performed and resource use described. No power calculation has been made.

Patient reported outcomes (PROMs)

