Patients will be included consecutively at each site during the enrollment window which is planned to be four years (2025–2029). Currently robotic-assisted spine surgery is available in two hospitals (Umeå and Örebro), with a third hospital waiting for their equipment to be installed (Uppsala). If other hospitals install robotic-assisted surgery during the study period this will just result in more patients involved in the robotic-assisted arm of the trial, which would result in a potentially faster inclusion of the needed amount of patients. We still believe that during the study period more patients will be operated with non-robotic-assisted methods than with robotic-assisted methods.

16–17. Allocation and blinding

No randomization or blinding will be performed. If a planned robotic-assisted surgery is abandoned after the start of surgery, the patient will be included in the robotic-assisted group (i.e. intention to treat principle).

18. Data collection methods

Data will be collected through national registries (Swespine, the Swedish Fracture Register, the Swedish PeriOperative Register, hospital systems (electronic health records, surgical planning software, Picture Archiving and Communication System; PACS and others). PROMs will be recorded preoperatively, and at follow-ups (Swespine: 1, 2 and 5 years; the Swedish Fracture Register: 1 year). Images will be retrieved using standardized CT protocols and assessment will be made by at least two researchers independently.

19. Data management

Data will be collected and managed in compliance with GDPR. Regular validation and updates will occur every 6–12 months. Final datasets will be stored at Uppsala University for a minimum of 15 years.

20. Statistical methods

Statistical analysis will compare outcomes using appropriate parametric or non-parametric tests,

including survival methods. Baseline characteristics will be adjusted for using multivariable models. Adjustment variables include age, diagnosis, comorbidities, previous spine surgery, number of levels, number of screws, robotic system type, use of navigation or free-hand surgery and hospital.

Analysis is currently planned to be performed in R. Interim analyses will be performed when half of the patients have been included. Sensitivity analyses will be performed as described earlier.

21. Data monitoring

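### Two of three robot centres already have the robot, but pre-study robotic cases are neither counted nor adjusted for: the precision split may be diluted, and the learning-curve case number has no defined origin

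*Protocol*

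**What the plan says.** **Robot availability (Protocol, section 15).** "Currently robotic-assisted spine surgery is available in two hospitals", namely Umeå and Örebro. Uppsala is still waiting for its equipment. Patients are included consecutively within an enrolment window, not from each centre's first robotic case. Section 15 gives the window as 2025–2029. Figure 2 shows inclusion from 2026, and section 2 dates the ethics approval to February 2026.

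**Learning curve (section 14, Substudy 2).** The Protocol states "we will model operative time as a function of case number", and the target is to "estimate the case number at which operative time levels off". The method is stated as "We will use mixed-effects piece-wise linear regression with the surgeon as a random effect". The analysis is expected "after each center has performed 100 robot-assisted spine surgeries, in total 300 surgeries". Neither the origin nor the unit of the case number is defined.

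**Screw placement precision (section 14, secondary outcome).** "We plan to use the first 60 cases in the study in each of 3 centers", divided into a first and a second group of 30 per centre. Here the origin is explicit: it is study order. Stratifying by surgeon experience is mentioned only as an option.

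**Prior experience.** Table 1 lists no count of earlier robotic cases, and the adjustment variables in section 20 include none.

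**The concern.** A learning curve is a function of accumulated experience. A surgeon who has done m robotic cases before inclusion enters the study at case m + 1 of that curve, while a surgeon at the third centre can enter at case 1. If both are labelled study case 1, different points on the curve are placed at the same position on the axis.

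This matters most in Substudy 2, because its primary result is itself a case number, which other hospitals could use when planning training. In the precision analysis, a first group that already contains experienced users differs less from the second group, so a real improvement with experience would look smaller than it is.

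**Working it through.** **The plan's own figures.** 100 × 3 = 300 surgeries for the learning curve. For precision, 60 × 3 = 180, split into 30 × 3 = 90 and 30 × 3 = 90. All reproduce. Substudy 2 has no power calculation, so there is no other figure to check.

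**Inputs.**
- From the Protocol: three robot centres, two with the robot available and one without; 100 cases per centre (learning curve); 60 per centre split 30/30 (precision).
- Assumed, because the Protocol does not give them: m prior cases at each of the two established centres (0 to 50) and none at the third; a linear fall to a plateau at lifetime case K = 30 or 50. For the breakpoint simulation also: a total fall of 60 minutes, residual SD 30 minutes, and one learning unit per centre.

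**Step 1: shift of the plateau.** Study case s at an established centre is lifetime case s + m. On the study axis the plateau is therefore at max(K − m, 0) there and at K in the third centre. With K = 30 and m = 10 this is 20, 20 and 30.

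**Step 2: precision contrast.** Let f(l) = max(K − l, 0)/K be the share of the learning effect still to come at lifetime case l. A centre's contrast is the mean of f over its study cases 1–30 minus the mean over cases 31–60. For K = 30 the second mean is always 0:
- m = 0: (29 + 28 + … + 0)/(30 × 30) = 435/900 = 0.483.
- m = 10: (19 + … + 0)/900 = 190/900 = 0.211 at the established centres. Over three centres: (2 × 0.211 + 0.483)/3 = 0.302.
- m = 20: (9 + … + 0)/900 = 45/900 = 0.050. Over three centres: (2 × 0.050 + 0.483)/3 = 0.194.
- m = 30 or more: 0 at the established centres. Over three centres: 0.483/3 = 0.161.

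**Step 3: fitted breakpoint if cases are counted from study entry.** Least-squares piece-wise linear fit with centre intercepts and one common breakpoint, 200 simulated data sets per row.

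| K | m | Plateau on study axis, established centres | Median common breakpoint (10–90% range) | Precision contrast, share of learning effect |
|---|---|---|---|---|
| 30 | 0 | 30 | 30 (25–35) | 0.48 |
| 30 | 10 | 20 | 24 (19–32) | 0.30 |
| 30 | 20 | 10 | 24 (11–42) | 0.19 |
| 30 | 30 | 0 | 29 (13–65) | 0.16 |
| 30 | 50 | 0 | 31 (17–56) | 0.16 |
| 50 | 0 | 50 | 50 (44–57) | 0.56 |
| 50 | 10 | 40 | 44 (36–51) | 0.49 |
| 50 | 20 | 30 | 37.5 (29–51) | 0.38 |
| 50 | 30 | 20 | 36 (22–54) | 0.27 |
| 50 | 50 | 0 | 51 (27–80) | 0.19 |

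The precision contrast falls, or stays at its floor, as m grows. The breakpoint does not move steadily. It is pulled down at moderate m. Once m reaches K, the established centres show no slope, the third centre alone locates the breakpoint, and the median returns near the truth with a much wider spread.

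**The case against.** Several stronger readings are tempting, and the Protocol does not support them.

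- **That the two centres have already been operating with the robot.** Section 15 says it is available and gives no case count. The background section says robotic spine surgery is not sanctioned outside clinical trials, and presents the study as an evaluation of clinical introduction. Prior use is plausible, since availability is stated before the ethics approval date, but it could be small or zero.
- **That the learning curve is counted in study cases.** The text does not say so. The timing rule refers to surgeries that each centre has performed, which is compatible with a lifetime count. Only the precision analysis ties itself to study order.
- **That earlier operative times cannot be obtained.** Nothing says this. The sources are registers, planning software and health records, and patient consent is not required.
- **That the plateau will come out too low.** The table shows no bias at m = 0 and, once m reaches K, imprecision rather than bias in the median.

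It can also be said that the origin of a counter, and whether breakpoints vary by surgeon, are details for an SAP, and that the Protocol allows for a curve already completed. The first part has some force, but prior counts are data that must be collected, and the precision rule is already fixed. Nor does a more flexible model solve the problem. A random intercept moves a surgeon's curve up or down, not sideways. Surgeon-specific breakpoints on the study axis would still estimate K − m for experienced surgeons: with K = 30 and m = 10, the average over one surgeon per centre is (20 + 20 + 30)/3 = 23.3. The clause on a completed curve applies only when no inflection appears, and a new third centre can produce one.

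**Conclusion.** The concern holds conditionally. For precision, the stated rule dilutes the early-versus-late contrast wherever the two established centres have robotic cases from before inclusion that fall on the improving part of the curve. With a plateau at 30, the contrast falls from 48% of the learning effect to 30% with 10 prior cases and 19% with 20. With a plateau at 50, it falls from 56% to 49% and 38%. For the learning curve, the fault is an undefined origin and unit. If counting starts at study entry, a true plateau of 30 gives a median breakpoint of 24 with 10 or 20 prior cases. With 50 prior cases and a plateau of 50, the median is 51 but the 10–90% range widens from 44–57 to 27–80.

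These sizes rest on assumed prior counts, an assumed curve shape and, for the breakpoint, assumed noise and a single common breakpoint. They are illustrations, not estimates for this study. If there were no earlier robotic cases, there is no bias, and a sentence saying so would settle the point. The change is worth making because the quantity at risk is a primary outcome and the remedy is cheap.

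**What to change.** 1. Define case number as each surgeon's cumulative number of robotic cases since that surgeon's first-ever one.
2. Obtain the pre-study count per surgeon from theatre or planning-system logs, and enter each study case at its true number in the Substudy 2 model.
3. Order the precision cases by the same count instead of by study order. The early and late groups may then no longer be exactly 90 and 90.
4. Add a sensitivity analysis restricted to surgeons whose first robotic case falls inside the study. This may leave few surgeons, possibly little beyond the third centre, so it should not replace the main analysis.

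The cost is a one-off log count per surgeon and a short addition to section 14.

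### Substudy 2 reads a missing inflection point as evidence about the learning curve, with no inconclusive outcome and no defined starting point for the case count

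*Protocol*

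**What the plan says.** Protocol section 14, Substudy 2, states the aim as "we will model operative time as a function of case number". The method is: "We will use mixed-effects piece-wise linear regression with the surgeon as a random effect to estimate the case number at which operative time levels off". On timing and size: "We expect to do this analysis after each center has performed 100 robot-assisted spine surgeries, in total 300 surgeries". The section says that no conventional power analysis was made, because the aim is estimation and not a test. It gives no target width for the breakpoint or the slope.

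The rule for a null result is: "If no clear inflection point is observed, this will be interpreted as evidence that the learning curve is either very short (already completed"; the sentence then adds very gradual and inconsistent as the other two options. Such a result is called informative in itself, and it triggers a comparison of operative times with navigated or freehand surgery.

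Section 15 says: "Currently robotic-assisted spine surgery is available in two hospitals", with the third centre still awaiting its equipment. For screw placement precision, a secondary outcome, section 14 says: "We plan to use the first 60 cases in the study in each of 3 centers". Those cases are split into a first and a second 30 per centre.

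The adjustment list in section 20 includes number of levels, number of screws, diagnosis and hospital. It does not include a surgeon's earlier robotic cases. Surgeon experience appears only as an optional stratifier for precision.

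**The concern.** Failing to locate a breakpoint is first of all a statement about how much information the data hold. If the interval for the breakpoint is wide, the result is inconclusive. The rule omits that outcome and assigns the null to one of three substantive readings. An estimation aim does not rescue it, because an imprecise estimate is not evidence for any of the three.

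The second problem is the time axis. The text does not say whether cases are counted per surgeon or per centre, or from the first robotic case ever or the first in the study. If surgeons at the two equipped centres did robotic cases before inclusion and these are not counted, case 1 means different things at different centres. The reading of very short, glossed as already completed, then merges two situations: a curve that is truly short, and one that was finished before observation began. Only the first says anything about how quickly the technique is learned. This is one of three primary objectives, so the wording matters.

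**Working it through.** **Plan's own figure.** 3 centres × 100 surgeries = 300, as stated. There is no power or precision figure for Substudy 2 to reproduce.

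**What uncounted cases do to the axis.** Let the true curve last K cases with total fall D, and let a surgeon have p uncounted earlier cases. On a study-based count the plateau then appears at case K − p, with a remaining fall of D × (K − p)/K. With assumed K = 30 and D = 60 minutes:

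- p = 0: plateau at case 30, 60 minutes visible.
- p = 15: plateau at 30 − 15 = 15, and 60 × 15/30 = 30 minutes visible.
- p ≥ 30: nothing visible. If this applies at two centres, 200 of the 300 cases are flat.

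**Illustration by simulation.** Taken from the protocol: three centres, 100 cases each, decline followed by plateau, surgeon effects. Assumed, not in the documents: K = 30, D = 60 minutes, residual SD 40 to 80 minutes, 1, 2 or 4 surgeons per centre, p earlier cases per surgeon at two centres, and counting from study start. The fit was within surgeon (centred on each surgeon's mean), with a grid search for the breakpoint. A clear inflection required a likelihood-ratio statistic above 5.99 against a flat line and above 3.84 against a straight line. These thresholds are crude. With 400 runs per setting, the simulation standard error is at most √(0.25/400) = 0.025.

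Share of runs with a clear inflection:

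| Surgeons per centre | SD (min) | p = 0 | p = 15 | p = 30 |
|---|---|---|---|---|
| 1 | 40 | 99% | 83% | 40% |
| 1 | 60 | 90% | 51% | 14% |
| 1 | 80 | 69% | 30% | 12% |
| 2 | 40 | 86% | 70% | 17% |
| 2 | 60 | 53% | 41% | 12% |
| 2 | 80 | 38% | 27% | 7% |
| 4 | 40 | 4% | 23% | 3% |
| 4 | 60 | 4% | 17% | 2% |
| 4 | 80 | 4% | 8% | 3% |

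Three things follow.

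1. *Hidden curve.* With one or two surgeons per centre, p = 30 sharply lowers detection of the same true curve. With p = 30, the share of runs with no decline seen at all is 41% to 79% for one surgeon per centre and 34% to 75% for two.
2. *Shortened curve.* With p = 15 and one or two surgeons per centre, the median breakpoint among runs showing a decline is 21 to 23, against 29 to 31 with p = 0.
3. *Too little data.* With four surgeons per centre, each has 100/4 = 25 cases, so every series ends before case 30. A clear inflection appears in only about 4% of runs even with no earlier cases. Here p = 15 raises detection, because it brings the plateau into view, but the median breakpoint is 16 to 18 instead of 30. The null at p = 0 reflects lack of data, which the rule does not list.

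**Does the planned fallback help?** A truly short curve and one completed before the study both give a flat series at the plateau level. Comparing that level with navigated or freehand times gives the same answer in both cases, so it cannot tell them apart.

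**The case against.** The strongest reply has four parts.

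- *The rule is a three-way statement.* Very gradual and inconsistent are not flattering readings, and a comparison with standard care follows. This stands as far as it goes: the rule does not by itself license a claim of a short curve. It still has no inconclusive outcome, and the comparison does not supply one.
- *Earlier use is not documented.* A reader might infer that two experienced centres and one inexperienced centre are being pooled. The documents do not support that. Section 15 says that robots are available and gives no counts. The background section says that robotic spine surgery is not sanctioned outside clinical trials. The protocol is dated 2025-12-01 and section 15 gives an enrolment window of 2025–2029, so current use may partly fall inside the study (Figure 2 appears to start inclusion in 2026). Earlier cases are possible, and their number is unknown.
- *The count may already be cumulative.* The Substudy 2 trigger of 100 surgeries per centre can be read as counting from first use, and a SAP may define the index. This stands: in Substudy 2 the origin is undefined, not shown to be wrong. Only the precision analysis explicitly counts from study entry; it has no rule for a null result and allows stratification by experience.
- *Case mix is covered.* A reader might also infer that the time model ignores case complexity. Section 20 already lists levels, screws and diagnosis for adjustment, so that is not part of this point.

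**Conclusion.** The point holds, and the change should be made. The interpretation rule is faulty as written, even if no surgeon had any earlier robotic case, because noise or too few cases per surgeon would be reported as evidence about the curve. The undefined case count is a smaller, conditional problem: if earlier cases exist and are not counted, the breakpoint can be hidden or placed too early.

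The documents do not determine the size. The percentages rest on assumed curve length, gain, residual SD, number of surgeons and earlier case counts, so they show direction only. A reader might go further and infer that the plan would report unrecorded experience as a completed, short curve. That does not follow, since the amount of earlier use is unknown and the rule keeps three readings open.

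**What to change.** 1. Replace the rule in section 14, Substudy 2. Report the breakpoint and the early slope with 95% CIs. Treat a missing inflection as inconclusive. Claim a short or absent curve only if the CI for the early slope excludes a minutes-per-case value stated in advance.
2. Define case number as each surgeon's cumulative robotic count from that surgeon's first ever robotic case. Take any pre-study counts from hospital records or SPOR, which the protocol already uses as data sources. Use the same index for the first-30/second-30 precision comparison.

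The cost is one reworded paragraph and retrieval of earlier counts at two hospitals. There are two downsides: the primary result of Substudy 2 may have to be reported as inconclusive, and the two precision groups may no longer hold exactly 30 × 3 = 90 cases each.
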